# A cluster randomised controlled trial of a whole school trauma-informed practice programme in secondary schools

## Statistical analysis plan

Evaluating institution: Anna Freud

Principal investigator(s): [name]

Project title	A cluster randomised controlled trial of a whole school trauma-informed practice programme in secondary schools
Developer (Institution)	Knowledge Change Action and Warren Larkin Associations Ltd
Evaluator (Institution)	Anna Freud
Principal investigator(s)	[name]
SAP author(s)	[name], [name], [name], [name], [name], [name], [name], [name], [name], and [name]
Trial design	Two-arm cluster randomized controlled trial, with a nested mixed methods convergence design qualitative-driven implementation and process evaluation
Trial type	Efficacy
Evaluation setting	Mainstream secondary schools
Target group	The programme is a whole school approach but the target group for the evaluation is Year 8 and Year 9 pupils (aged 12-14 years) and school staff
Number of participants	Numbers of pupils reached by the programme = 35,000-47,818 pupils across year groups in 50 schools

	
Optimal sample size for the evaluation = 18,649 Year 8 and 9 pupils in 100 schools
 
Optimal sample size for the evaluation (school staff) = 15,867

Primary outcome and data source
	
Externalising difficulties measured with the sum of the conduct problems and hyperactivity subscales of the Strengths and Difficulties Questionnaire (Goodman, Meltzer, & Bailey, 1998)


Secondary outcome and data source
	
Pupil-reported surveys
 
Measure A: Strengths and Difficulties Questionnaire (Goodman et al., 1998)
 
Outcomes: mental health difficulties, prosocial behaviour
 
Variables: 1) internalising difficulties, 2) impact score, 3) prosocial behaviour
 
Measure B: Student Engagement Instrument (Appleton et al., 2006)
 
Outcomes: safe social connection(s) with teachers, safe social connection(s) with peers, school inclusion
 
Variables: 4) teacher-student relationships, 5) peer support for learning, 6) control and relevance of school work, 7) future aspirations and goals
 
Measure C: Illinois Bully Scale (Espelage & Holt, 2001)
 
Outcome: bullying
 
Variable: 8) bullying perpetration, 9) bullying victimisation
 
Staff-reported surveys
 
Measure A: Attitudes Related to Trauma-Informed Care (ARTIC 35) (Baker et al., 2021)
 
Outcomes: knowledge and awareness, confidence, emotionally safe environment, vicarious trauma, empathy-focussed behaviours

	
Variables: 1) underlying causes of problem behaviour and symptoms, 2) self-efficacy at work, 3) response to problem behaviour, 4) reactions to work, 5) empathy and control
 
Measure B: Professional Quality of Life Scale (ProQOL) (Stamm, 2010)
 
Outcomes: wellbeing, burnout
 
Variables: 6) compassion satisfaction, 7) compassion fatigue, 8) burnout
 
Local school data (and National Pupil Database for longer-term outcomes)
 
Outcome: school attendance and exclusions
 
Variables: 1) attendance, 2) exclusions, 3) permanent exclusions

--	--

## Introduction

More Good Days At School (MGDAS) is a two-arm cluster randomised controlled trial. The trial is an evaluation of a whole-school trauma-informed practice programme, which focuses on training and capacity building for all school staff in understanding the impact of trauma, the importance of staff-pupil relationships, relational approaches, and strategies to look after one's own mental health.

The school is the unit of randomisation: half of the schools were randomised to receive the training, and half were to continue with existing wellbeing support practices at the school. The evaluation is focused on year 8 pupils, year 9 pupils and school staff. Schools were randomised in two cohorts: cohort 1 in November 2023 and cohort 2 in February 2024. Randomisation was stratified by Local Authority (LA) or Combined Authority (CA), with a minimum of two schools needed for LA/CA to be included in the randomisation.

There are three data collection periods: baseline, mid-programme (approximately 5 months after randomisation), and end of programme (after training is complete: approximately 16 months after randomisation). Data collection periods were coordinated between cohorts so that they occurred at the same stages for training inputs.

The primary outcome measure is externalising difficulties, as measured by the sum score of the conduct problems and hyperactivity subscales of the Strengths and Difficulties Questionnaire (Goodman et al., 1998). Secondary outcome measures are related to pupil and teacher wellbeing and school connections; the variables and measures are listed in detail in the Design Overview.

The main purpose of the analysis is to evaluate the impact of whole-school trauma-informed practice training on primary and secondary outcome measures for staff and pupils. Additional analyses will be conducted to test for differential effects of whole-school trauma-informed practice training, such whether the effect of training differs by ethnicity, free school meal (FSM) eligibility, special educational needs and disabilities (SEND) or Education, Health and Care Plan (EHCP) status, year group, and staff-reported empathy and control. In addition, analyses will be conducted to clarify the mechanisms by which training impacts pupil outcomes, such whether safe social connections with teachers mediates the relationship between training and pupil's externalising difficulties.

## Design overview

Trial design, including number of arms		Two-arm cluster randomized controlled trial
Unit of randomisation		Cluster (school)
Stratification variables (if applicable)		Local Authority or Combined Authority
Primary outcome	variable	Externalising difficulties
	measure (instrument, scale, source)	Sum of the conduct problems and hyperactivity subscales of the Strengths and Difficulties Questionnaire (Goodman et al., 1998)
Secondary outcome(s)	variable(s)	
Pupil-reported surveys
 
Variables: 1) internalising difficulties, 2) impact score, 3) prosocial behaviour
 
Variables: 4) teacher-student relationships, 5) peer support for learning, 6) control and relevance of school work, 7) future aspirations and goals
 
Variable: 8) bullying perpetration, 9) bullying victimisation
 
Staff-reported surveys
 
Variables: 1) underlying causes of problem behaviour and symptoms, 2) self-efficacy at work, 3) response to problem behaviour, 4) reactions to work, 5) empathy and control
 
Variables: 6) compassion satisfaction, 7) compassion fatigue, 8) burnout
 
Local school data

		
Variables: 1) attendance, 2) fixed-term exclusions, 3) permanent exclusions

	
measure(s) (instrument, scale, source)
	
Pupil-reported surveys
 
Measure A: Strengths and Difficulties Questionnaire (Goodman et al., 1998)
 
Outcomes: mental health difficulties, prosocial behaviour
 
Variables: 1) internalising difficulties, 2) impact score, 3) prosocial behaviour
 
Measure B: Student Engagement Instrument (Appleton et al., 2006)
 
Outcomes: safe social connection(s) with teachers, safe social connection(s) with peers, school inclusion
 
Variables: 4) teacher-student relationships, 5) peer support for learning, 6) control and relevance of school work, 7) future aspirations and goals
 
Measure C: Illinois Bully Scale (Espelage & Holt, 2001)
 
Outcome: bullying
 
Variable: 8) bullying perpetration, 9) bullying victimisation
 
Staff-reported surveys
 
Measure A: Attitudes Related to Trauma-Informed Care (ARTIC 35) (Baker et al., 2021)
 
Outcomes: knowledge and awareness, confidence, emotionally safe environment, vicarious trauma, empathy-focussed behaviours
 
Variables: 1) underlying causes of problem behaviour and symptoms, 2) self-efficacy at work, 3)

		
response to problem behaviour, 4) reactions to work, 5) empathy and control
 
Measure B: Professional Quality of Life Scale (ProQOL) (Stamm, 2010)
 
Outcomes: wellbeing, burnout
 
Variables: 6) compassion satisfaction, 7) compassion fatigue, 8) burnout
 
Local school data
 
Outcome: academic attendance and exclusions
 
Variables: 1) attendance, 2) fixed-term exclusions, 3) permanent exclusions

Baseline for primary outcome	variable	Externalising difficulties
	measure (instrument, scale, source)	Conduct problems and hyperactivity subscales of the Strengths and Difficulties Questionnaire (Goodman et al., 1998)
Baseline for secondary outcome	variable	
Pupil-reported surveys
 
Variables: 1) internalising difficulties, 2) no baseline for impact score, 3) prosocial behaviour
 
Variables: 4) teacher-student relationships, 5) peer support for learning, 6) control and relevance of school work, 7) future aspirations and goals
 
Variable: 8) bullying perpetration, 9) bullying victimisation
 
Staff-reported surveys
 
Variables: 1) underlying causes of problem behaviour and symptoms, 2) self-efficacy at work, 3) response to problem behaviour, 4) reactions to work, 5) empathy and control

		
Variables: 6) compassion satisfaction, 7) compassion fatigue, 8) burnout
 
Local school data
 
Variables: 1) attendance, 2) fixed-term exclusions, 3) no baseline for permanent exclusions (given their relatively low frequency)

	
measure (instrument, scale, source)
	
Pupil-reported surveys
 
Measure A: Strengths and Difficulties Questionnaire (Goodman et al., 1998)
 
Outcomes: mental health difficulties, prosocial behaviour
 
Variables: 1) internalising difficulties, 2) no baseline for impact score, 3) prosocial behaviour
 
Measure B: Student Engagement Instrument (Appleton et al., 2006)
 
Outcomes: safe social connection(s) with teachers, safe social connection(s) with peers, school inclusion
 
Variables: 4) teacher-student relationships, 5) peer support for learning, 6) control and relevance of school work, 7) future aspirations and goals
 
Measure C: Illinois Bully Scale (Espelage & Holt, 2001)
 
Outcome: bullying
 
Variable: 8) bullying perpetration, 9) bullying victimisation
 
Staff-reported surveys
 
Measure A: Attitudes Related to Trauma-Informed Care (ARTIC 35) (Baker et al., 2021)

		
Outcomes: knowledge and awareness, confidence, emotionally safe environment, vicarious trauma, empathy-focused behaviours
 
Variables: 1) underlying causes of problem behaviour and symptoms, 2) self-efficacy at work, 3) response to problem behaviour, 4) reactions to work, 5) empathy and control
 
Measure B: Professional Quality of Life Scale (ProQOL) (Stamm, 2010)
 
Outcomes: wellbeing, burnout
 
Variables: 6) compassion satisfaction, 7) compassion fatigue, 8) burnout
 
Local school data
 
Outcome: academic attendance and exclusions
 
Variables: 1) attendance, 2) fixed-term exclusions, 3) no baseline for permanent exclusions (given their relatively low frequency)

--	--	---

## Sample size calculations overview

		Protocol	Randomisation
Minimum Detectable Effect Size (MDES)		Standardised mean difference = 0.15	Standardised mean difference = 0.17
Pre-test/ post-test correlations	level 1 (participant)	-	-
	level 2 (cluster)	-	-
Intracluster correlations (ICCs)	level 1 (participant)	0.03	0.041
	level 3 (cluster)	-	-
Alpha		0.05	0.05
Power		0.8	0.8
One-sided or two-sided?		Two-sided	Two-sided
Average cluster size		186 pupils 159 staff	220 pupils 26 staff
Number of clusters	intervention	29	31
	control	29	31
	total	58	62

		Protocol	Randomisation
Number of participants	intervention	4650 pupils 3975 staff	6429 pupils 724 staff
	control	4650 pupils 3975 staff	7194 pupils 896 staff
	total	9300 pupils 7950 staff	13623 pupils 1620 staff

The cluster sample size was determined a priori using a minimum detectable effect size (MDES) of 0.15 (standardised mean difference). The protocol presented different scenarios for sample size calculations based on a MDES between 0.10 and 0.20 (see Table 4 in the trial protocol). Presented in the table above is the sample size calculation for MDES of 0.15, which is in line with a projected school recruitment of 55 schools inflated to account for 15% attrition (58 in total). The estimate for the mean and SD of externalising difficulties in the control arm was based on the combined female and male scores from Elia et al. (2020). The intraclass correlation coefficient was assumed as 0.03. There is a lack of evidence on which to base assumptions for the pre-post correlation of externalising difficulties, so the sample size calculations were not adjusted to account for this. STATA was used for the power calculation using the following code: (MDE 0.15) power twomeans 5.21 4.76, sd(2.96) rho(0.03) m1(186) m2(186) power(0.8) cvcluster(0.5) cluster = 25 schools and 4,650 pupils per arm (increased to 29 schools per arm based on 15% school attrition).

The primary population of interest is pupils; estimates are also presented for staff. The pupil and staff sample sizes were determined from figures from three initial Local Authorities (LAs; Kent, Slough and Wiltshire). From this, 186 pupils per school were assumed after accounting for 35% study refusal and 25% attrition, resulting in an estimated sample size of 9300 pupils in total. 159 staff per schools were assumed after accounting for 35% study refusal and 25% attrition, resulting in 7950 staff in total.

The section with actual sample size and MDES at randomisation were updated following randomisation in February 2024. The average cluster size for pupils who completed the

primary outcome (SDQ externalising symptoms items) was 219.73, rounded to 220 pupils in the table. Furthermore, intracluster correlation was calculated as 0.041 and coefficient of variation was 0.366. With these parameters, we are powered to detect MDES of 0.17. Please see the following STATA code, which estimates the number of schools as 24.3 and the number of pupils per arm as 5333.02, inflated to 29 schools and 6372 pupils per arm based on 15% school attrition: `power twomeans 5.21 4.7, sd(2.96) rho(0.041) m1(219.73) m2(219.73) power(0.8) cvcluster(0.366) nfrac display "schools per arm = " ceil(r(K1)/.85) display "pupils per arm = " round(ceil(r(K1)/.85)*219.73).`

## Analysis

Analyses will be conducted by an analyst masked to intervention group assignment following the intention-to-treat principle. The hypotheses and general analysis framework were decided a priori; the analysis plan was written and finalised during the period of data collection after recruitment but before baseline data collection was completed. The analyses will use maximum likelihood estimation meaning all participants will be included, even those with missing follow up data points, in line with the intention-to-treat principle. There will be two approaches to handling missing data, assuming that data are missing at random: 1) multiple imputation of data at any time point using wide format data, and 2) participants who have at least one post-randomisation observation will be included in the model with maximum likelihood estimation. Results will be compared using the two approaches. The chosen analysis model to assess the intervention effect is a mixed effects model. This model will form the basis of the main trial report that will be submitted for publication. Fixed effects will include group allocation (intervention/control), time (mid-programme/end of programme), and the interaction between group allocation and time. Random intercepts for pupils or staff nested within schools will also be specified, depending on whether the outcome is pupil- or staff-specific. The baseline level of the outcome will be included as a covariate to increase power and precision. Cohort (1/2), year group (8/9) and gender (dummy coded: male/female/gender diverse, reference: male) will be included as fixed effect prognostic factors to improve precision of the treatment effect. LA/CA was used as a stratifier in the randomisation, and it is intended to be included in the analysis as a fixed effect. However, there may be issues with model estimation due to a small number of schools per LA/CA (minimum of two). In this case, we will specify a three-level model (pupil, school, LA) or remove LA/CA as a fixed effect from the analysis. For the mixed effects models, the package *lme4* version (version 1.1-35.1) in R will be used (Bates et al., 2015). Interaction terms will be specified within the mixed effects models. Example syntax for the primary outcome of pupil externalising symptoms with LA/CA included as a fixed effect is:

```
lmer(externalising ~ group * time + (1 + school | pupil) + baseline_externalising + cohort_1_2 + year_group_8_9 + male_female + male_diverse + LA_CA, data = MGDAS_data)
```

Subgroup analyses and further analyses are detailed in the relevant sections below.

Standard data quality checks will be performed in the data preparation stage before analysis, including impossible values, distribution of scores and residuals, outliers, low frequency categorical variables, linearity, and homogeneity of variance. Violations will be managed with

appropriate techniques. Descriptive statistics of the implementation data will be used to identify levels of implementation and engagement.

There are no planned interim analyses for efficacy.

This project contains multiple secondary outcomes and analyses. For pupils, there are 16 secondary outcomes, and, for staff, there are 7 secondary outcomes. As a result, there is a higher risk of false positives overall. To mitigate this, false discovery rate (FDR) multiple comparison correction will be applied to the significance level for tests for outcomes that are within the same measure, as these are likely to be correlated both theoretically and statistically. For example, FDR correction will be applied to three SDQ secondary pupil outcomes. In a similar vein, FDR correction will be applied to subgroup and further analyses. Some of these analyses will be underpowered, increasing the chance of false negatives in some cases. All exploratory analyses must therefore be treated with caution and not interpreted individually.

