### **Missing data**

We will explore the amount of missingness in the data, such as the percentage of missing values per variable. We will evaluate the extent to which data are systematically missing by investigating which baseline variables are associated with missingness for the primary outcome of externalising symptoms at the end of programme time point. Multi-level logistic regression will be conducted to identify variables that predict missingness (0 = not missing, 1 = missing).

Intervention schools that have withdrawn post-randomisation will still be asked to participate in the follow-up data collection periods, to minimize missing data and the need for imputation.

We will have two approaches to addressing missing data and we will compare the results between approaches:

- 1) Multiple imputation will be conducted for any baseline and follow up data. Data will be imputed with data in wide format without clustering for time, as time will be included as a dummy coded variable in the analysis. The package *mice* will be used to impute missing values (van Buuren & Groothuis-Oudshoorn, 2011). The quickpred

function within mice will be used with a minimum correlation of 0.25 to build the predictor matrix for imputation. School will also be specified as a predictor in the predictor matrix. At least 25 imputations will be specified; the number of imputations will match the percentage of missing data. Analyses will be run with these datasets with the pooled estimates derived.

- 2) Participants with at least one post-randomisation datapoint (i.e. mid-programme or end of programme) will be included and analyses will be run with maximum likelihood estimation.

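### The SAP says maximum likelihood includes all participants, but that analysis requires a follow-up score and, by default, a baseline score, so its analysis set differs from that of the imputed analysis

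*SAP*

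**What the plan says.** The Analysis section of the SAP makes a general claim: "The analyses will use maximum likelihood estimation meaning all participants will be included, even those with missing follow up data points". It presents this as following the intention-to-treat principle.

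It then sets out two approaches to missing data, both assuming data missing at random.

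- **Approach 1, multiple imputation.** The Missing data section says: "Multiple imputation will be conducted for any baseline and follow up data".
- **Approach 2, maximum likelihood.** The Analysis section says: "participants who have at least one post-randomisation observation will be included in the model with maximum likelihood estimation". The Missing data section repeats the rule: "Participants with at least one post-randomisation datapoint (i.e. mid-programme or end of programme) will be included".

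Of the two, the Analysis section says: "Results will be compared using the two approaches". Neither is named as primary.

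The fixed effects include "time (mid-programme/end of programme), and the interaction between group allocation and time", so baseline is not an outcome occasion. Instead, "The baseline level of the outcome will be included as a covariate to increase power and precision". The example `lmer` code has `baseline_externalising` on the right-hand side. The equation under Primary outcome analysis omits baseline, but the text and the code both include it.

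Gender is specified as "gender (dummy coded: male/female/gender diverse, reference: male"), and enters the code as two dummies, `male_female` and `male_diverse`. Table 1 has a separate 'Prefer not to say' row for gender. Under Subgroup analyses the same answer is listed among the ethnicity categories to be dummy coded; no such statement is made for gender.

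**The concern.** The general claim and the rule for approach 2 cannot both be true. A model whose only outcomes are the mid-programme and end-of-programme scores receives no outcome from a participant with neither. The phrase about missing follow-up points holds only for someone who lacks one of the two.

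The less visible loss is the baseline score. Maximum likelihood in this model accommodates missing outcomes. It places no distribution on the covariates, so it cannot accommodate a missing one. A pupil absent from the baseline survey who answers both follow-ups satisfies the written rule for approach 2, yet is removed when the code is run. Observed post-randomisation outcomes are then discarded in an analysis described as intention-to-treat. If such pupils differ from the rest, the estimate may be biased. Approach 1 keeps them, so a difference between the two results would mix the handling of missing values with a change in who is analysed. The SAP has no rule for which result then stands.

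**Working it through.** **Who is analysed under each approach**

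| Baseline score | Follow-up scores | Approach 1 | Approach 2, written rule | Approach 2, as coded |
|---|---|---|---|---|
| present | one or two | in | in | in |
| present | none | can be kept (outcomes imputed) | out | out |
| missing | one or two | can be kept (baseline imputed) | in | deleted by default |

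The second row contradicts the general claim. The third contradicts both that claim and the written rule for approach 2. The SAP plans to impute baseline data, so it expects some participants in the third row.

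**Size of the no-follow-up group.** Table 1 has 6,429 + 7,194 = 13,623 pupils, all with a complete baseline externalising score. The sample size section allows 25% attrition. Reading that as loss of both follow-ups is an assumption, so a range is shown:

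- 5%: 0.05 × 13,623 = 681
- 25%: 0.25 × 13,623 = 3,406

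**Size of the no-baseline group.** The SAP does not give it, and it cannot be taken from Table 1, which holds baseline completers only. As an assumed range, let a be the share of participants with no follow-up (5% to 25%) and b the share of the remainder with no baseline (0% to 20%). Approach 2 keeps (1 − a)(1 − b):

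- 0.95 × 1.00 = 95%
- 0.75 × 0.80 = 60%

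These limits illustrate the calculation and are not estimates.

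**Undisclosed gender.** 145 (intervention) + 127 (control) = 272, and 272/13,623 = 2.0%. By arm this is 145/6,429 = 2.3% and 127/7,194 = 1.8%. The gender rows sum to 6,429 and 7,194, so no pupil in Table 1 has a blank answer. Non-binary, questioning and other together number 51 + 46 + 58 + 64 + 52 + 59 = 330. Placing the 272 in the gender-diverse level would make it 602.

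**Power.** The plan's own figure comes first. Inputs from the sample size section: difference 5.21 − 4.70 = 0.51, SD 2.96, ICC 0.041, m = 219.73, CV 0.366, two-sided alpha 0.05, power 0.80.

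- Unclustered n per arm = 2 × (2.96 × (1.960 + 0.842)/0.51)² = 528.8
- Design effect = 1 + (219.73 − 1) × 0.041 = 9.968
- Relative efficiency = 1 − CV² × L × (1 − L) = 0.9884, with L = m × ICC/(m × ICC + 1 − ICC)
- Pupils per arm = 528.8 × 9.968/0.9884 = 5,333.03 (unrounded inputs); the SAP states 5333.02
- Schools per arm = 5,333.03/219.73 = 24.27; the SAP states 24.3. Then 24.27/0.85 rounds up to 29, as stated.

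The figure reproduces. With the 31 schools per arm actually randomised, the detectable effect is (1.960 + 0.842) × √(2 × design effect/(relative efficiency × 31 × m)):

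- m = 219.73: 0.152 SD
- m = 0.75 × 219.73 = 164.80: 0.155 SD

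**The case against.** The rule requiring at least one follow-up score is stated openly in two sections. A participant with no outcome adds nothing to this likelihood whether or not they are called included. Under the stated missing-at-random assumption, imputing outcomes for such participants adds little without auxiliary variables. Missing baseline scores are handled in approach 1, and which records each approach can use is partly a feature of the method. All of this stands. It makes the no-follow-up limb mainly a matter of a wrong sentence. It does not answer the missing-baseline limb: approach 2 loses observed outcomes, and the SAP gives no other handling for them.

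A reader might infer more than the document supports:

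- **That pupils with undisclosed gender are dropped.** The SAP does not say so. With the two dummies they could become missing, gender diverse, or zero on both and so counted as male. Nor would approach 1 impute a recorded answer unless it were first recoded as missing. What can be said is that the coding is unspecified.
- **That the two approaches concern different populations.** Under missing at random both can target the same effect. What differs is the analysis set.
- **That those missing at baseline have high externalising scores.** This is plausible, but the SAP gives no data on them.
- **That missing year group for cohort 1 is a further loss.** It is due from school administrative data.

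**Conclusion.** The concern holds in a limited form. The statement that maximum likelihood includes all participants is false for approach 2, for two reasons: the written follow-up requirement, and the default deletion of anyone without a baseline score. The two analyses to be compared therefore rest on different analysis sets without saying so, and neither is named as primary.

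The size cannot be fixed from the SAP. The no-follow-up counts depend on an assumed share, and the number without a baseline score is not reported. The deletion presumes that `lmer` is run with its default treatment of missing covariates, as nothing else is specified. Loss of power is not the issue. What remains is an intention-to-treat description that the analysis does not meet and a possible bias of unknown size. The uncoded gender answer is a smaller, separate gap affecting 2.0% of pupils in Table 1.

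**What to change.** - Replace the sentence about all participants with one stating that approach 2 includes every consented participant, pupil or staff, with at least one follow-up score.
- In approach 2, keep those without a baseline score. Either fill the baseline with the mean and add a missing indicator, or model baseline as a response alongside the two follow-ups with arm means constrained equal at baseline.
- Name which approach is primary.
- Report the numbers per arm in each analysis, since the sets may still differ for participants with no follow-up.
- State how 'Prefer not to say' on gender is coded, for example as its own level.

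Redefining both analyses on all pupils enrolled at randomisation is not advised. Neither baseline option above would deliver that set, and it could take in pupils who declined the study, for whom the sample size section allows 35% refusal.

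The cost is SAP wording, a few lines of code and one or two extra model parameters. No new data are needed.

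### The prose specifies maximum likelihood with LA/CA fixed effects, the example code implies REML, and no small-sample reference is named for the school-level group contrast

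*SAP*

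**What the plan says.** The relevant statements are all in the SAP.

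- **Estimator, prose (Analysis):** "The analyses will use maximum likelihood estimation meaning all participants will be included". The stated reason is to keep participants with incomplete follow-up. The Missing data section names maximum likelihood again for its second approach.
- **LA/CA (Analysis):** "LA/CA was used as a stratifier in the randomisation, and it is intended to be included in the analysis as a fixed effect". The plan then adds a caution: "However, there may be issues with model estimation due to a small number of schools per LA/CA (minimum of two". If estimation proves difficult, LA/CA becomes a third level or is removed.
- **Code (Analysis, example syntax):** the call begins "lmer(externalising ~ group * time + (1 + school | pupil", lists LA/CA among the fixed terms and carries no REML argument. lmer fits by REML unless told otherwise.
- **Equation (Primary outcome analysis):** the text describes three levels and calls them fixed effects. The equation writes LA/CA as a term v and school as a term u, with no LA/CA dummies.
- **Test level (Sample size calculations overview):** alpha 0.05, two-sided, with 31 schools per arm.
- **Effect size (Presentation of outcomes):** the numerator is the adjusted mean difference at each time point. Intervals are to be bootstrapped, with type and resampling level not stated.

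No section mentions REML, Satterthwaite, Kenward-Roger or any other reference distribution for the group contrast. The number of LA/CAs randomised is not given.

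**The concern.** Allocation varies only between schools, so the precision of a group difference at a time point rests on the school-level variance, estimated from 62 schools. ML estimates that variance without allowing for the fixed effects fitted at school level. Each LA/CA dummy is such an effect, so the more LA/CAs there are, the more the school variance and the standard error of the group difference are understated. REML makes the allowance.

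The reference distribution is a second, smaller matter. lme4 prints no p-value, so the analyst must choose one. The usual view that 62 clusters are enough for a normal reference does not count the degrees of freedom used by LA/CA, which could leave as few as 30.

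Two analysts following this SAP, one by the prose and one by the code, would therefore fit different estimators and could reach different conclusions on the primary outcome.

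**Working it through.** **1. The plan's own figure.** The inputs come from "power twomeans 5.21 4.7, sd(2.96) rho(0.041) m1(219.73) m2(219.73) power(0.8) cvcluster(0.366) nfrac".

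- Individually randomised n per arm = 2 × (2.96 × (1.960 + 0.842) / 0.51)² = 528.8.
- Design effect = 1 + (219.73 − 1) × 0.041 = 9.968, giving 528.79 × 9.968 = 5270.9 pupils.
- Unequal cluster sizes: λ = 219.73 × 0.041 / (219.73 × 0.041 + 0.959) = 0.904. Relative efficiency = 1 − 0.366² × 0.904 × 0.096 = 0.988.
- 5270.9 divided by the unrounded relative efficiency is 5333.03 pupils, or 24.27 schools per arm. Then 24.27 / 0.85 rounds up to 29 schools, and 29 × 219.73 = 6372 pupils.

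This agrees with the SAP's 24.3 schools, 5333.02 pupils, and 29 schools with 6372 pupils after attrition. The sample size is not in question here.

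**2. Error rate for the group difference at a time point.** Inputs: K = 62 schools (SAP) and L LA/CAs. L is not given. With at least two schools in each, L is at most 62 / 2 = 31. The school-level fixed effects are the L LA/CA parameters (including the intercept) and group, so df = K − L − 1.

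- ML variance of a school mean ≈ (df / K) × the unbiased value.
- ML with a normal reference: error = P(|t_df| > 1.96 × √(df / K)).
- REML with a normal reference: error = P(|t_df| > 1.96).
- REML with t on df: 5% by construction in the balanced case.

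For example, with L = 10, df = 51, df / K = 0.823 and √0.823 = 0.907. The effective cut-off is 1.96 × 0.907 = 1.78, and P(|t_51| > 1.78) = 8.1%.

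| LA/CAs | df | df / K | SE ratio | ML, normal | REML, normal | ML, t |
|---|---|---|---|---|---|---|
| removed | 60 | 0.968 | 0.984 | 5.9% | 5.5% | 5.4% |
| 5 | 56 | 0.903 | 0.950 | 6.8% | 5.5% | 6.2% |
| 10 | 51 | 0.823 | 0.907 | 8.1% | 5.6% | 7.5% |
| 20 | 41 | 0.661 | 0.813 | 11.9% | 5.7% | 10.8% |
| 31 | 30 | 0.484 | 0.696 | 18.3% | 5.9% | 16.6% |

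The last two columns separate the causes. Changing only the reference distribution leaves most of the inflation, while changing only the estimator removes most of it. Counting cohort as one more school-level parameter moves the ML figures up slightly, for example from 8.1% to 8.5% at L = 10.

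With 52 schools (about 15% lost), ML with a normal reference gives 7.2%, 8.9% and 14.0% for 5, 10 and 20 LA/CAs.

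**3. Check by simulation.** 1,500 runs per setting, 62 schools of unequal size (assumed mean 186 pupils, CV 0.366), at ICC 0.041 and 0.015.

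- ML, normal reference: 4.7% and 6.4% with no LA/CA effects; 7.3% and 7.4% (10 LA/CAs); 10.9% and 12.1% (20); 19.6% at both ICCs (31).
- REML, normal reference: 4.2% to 6.8% across all settings.
- REML, t reference: 3.9% to 5.6%.
- ML school variance as a share of the truth at ICC 0.041: 0.79, 0.60 and 0.41 for 10, 20 and 31 LA/CAs. For REML it is 0.98 to 1.00.

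Simulation error is about ±1 point near 5% and ±2 points near 20%.

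**4. What the code adds.** All these figures suppose a school random intercept, as the prose describes. The printed random term, `(1 + school | pupil)`, does not contain one, so REML and degrees of freedom applied to that call would still not account for clustering by school.

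**The case against.** The strongest reply is that the plan does not really choose ML as a variance estimator. Both mentions concern retaining incomplete records, which REML does equally well, and the only executable specification would run at the REML default. On that reading, once a school intercept is in the model, the error is about 5.5% to 6% even with a normal reference. This stands in part. It shows that the plan contradicts itself and does not clearly fix ML. It does not show that an analyst following the prose would avoid ML.

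Three further points stand as limits:

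- **The normal reference is an assumption.** The SAP names no test, and silence is not a choice of a z test. The bootstrapped intervals do not settle the matter, because they are specified for the effect size and their type is unstated.
- **The large figures need many LA/CAs and the dummies kept.** The plan allows LA/CA to become random or be removed. That fallback depends on estimation difficulty and not on the number of LA/CAs, so it reduces the problem without guaranteeing protection.
- **The contrast matters.** The plan does not say which coefficient carries the 5% test. The mechanism applies to the group difference at a time point. In the group-by-time interaction the school intercept largely cancels, and these figures do not carry over.

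A reader might infer that the primary test is known to run at 18%. The documents do not support that: it requires ML, a normal reference and exactly two schools in each of 31 LA/CAs, all together.

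**Conclusion.** The point holds as an unresolved specification with a potentially material effect. Prose and code imply different estimators, and nothing fixes the reference distribution for a contrast that rests on 62 schools.

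If the prose is followed with a normal reference, the error exceeds the stated 5% at every possible number of LA/CAs: slightly if LA/CA is dropped (about 5.9%), clearly at 10 (8.1%), and severely at the limit of 31 (18.3%). If REML is used with a normal reference, the excess is at most about one point analytically. ML combined with many LA/CA dummies is the main driver; the missing degrees of freedom alone are minor.

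It would go too far to say that the primary analysis is invalid as planned. The estimator is ambiguous, the number of LA/CAs is unknown, and the fallback may apply. The figures rest on a school-level approximation for a group difference at a single time point and on a correctly specified school intercept. The random-LA/CA fallback was not computed separately.

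**What to change.** - State that the confirmatory mixed models are fitted by REML. It uses the same observed records under missing at random, so the reason given for maximum likelihood is fully met. Keep ML only for likelihood-ratio comparisons of fixed effects.
- State that the group difference at each time point is tested with Satterthwaite or Kenward-Roger degrees of freedom.
- Fix how LA/CA enters the model and report the number of LA/CAs.
- Align prose, equation and code. The lmer call needs a school random intercept, for example `(1 | school/pupil)`. Without it, the first two changes do not protect the test.

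The cost is a few sentences, a corrected call and one additional package for the degrees of freedom. Intervals become somewhat wider. Relative to ML, the standard error grows by 1 / 0.950 = 1.05 with 5 LA/CAs and 1 / 0.907 = 1.10 with 10, and by more if there are many. That widening is the correction itself and not a loss of information. No new data are needed.
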